6.1.4.2 Proportion of malaria positive children prescribed an antimalarial

A malaria test will be considered positive if a malaria test was ordered during the consultation and was recorded as positive. If the test result is invalid/indeterminate, reported but handwriting not readable or not sure/not reported, the test will not be considered positive.

The child will be considered prescribed with an antimalarial if:

- ξ One or more antimalarial drugs were selected from the antimalarial/treatment drop-down list
- ξ Antimalarial drugs were not selected from the antimalarial/treatment drop-down list but antimalarial drugs were listed in the free text field (conditional to feasibility of assessing free text)

Only children with a positive malaria test result will be counted in the denominator.

6.1.4.3 Proportion of malaria negative children prescribed an antimalarial

A malaria test will be considered negative if a malaria test was ordered during the consultation and the result was negative. If the test result is invalid/indeterminate, or handwriting not readable or not sure/not reported, the test will not be considered negative.

Antimalarial drug prescription will be assessed as described in the point above.

Only children with a negative malaria test result will be counted in the denominator.

6.1.4.4 Proportion of untested children prescribed an antimalarial

A child will be considered untested for malaria if, a malaria test was not ordered during the consultation or a malaria test was ordered during the consultation but a test result is not available.

Antimalarial drug prescription will be assessed as described in the point above.

Only children untested for malaria will be counted in the denominator.

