3.1.4 Outcomes

This section provides an overview of the outcomes as listed in the protocol.

Primary outcomes

- ξ Proportion of children with a severe complication by Day 7
- ξ Proportion of children admitted to hospital within 24 hours of the Day 0 consultation and as a result of a referral (this is a proxy for 'appropriate referral' of children)

Secondary outcomes

- ξ Proportion of children with a severe complication by Day 28
- ξ Proportion of children cured at Day 7 follow-up
- ξ Proportion of children referred by a primary healthcare provider to a higher level of care at Day 0 consultation
- ξ Proportion of children who completed referral as reported at Day 7 follow-up

Other outcomes of interest – hypoxaemia (in intervention arms only)

- ξ Proportion of children with severe ($\text{SpO}_2 < 90\%$), moderate ($\text{SpO}_2 90 - 91\%$) and mild ($\text{SpO}_2 92 - 93\%$) hypoxaemia, adjusted for sites at high altitude
- ξ Proportion of children with hypoxaemia (according to differing cut-offs) with severe complication

- § Proportion of children with severe hypoxaemia not meeting any other clinical criteria for severe disease
- § Proportion of children referred with hypoxaemia who receive oxygen at hospital

Other outcomes of interest – referral and follow-up

- § Proportion of children with non-severe disease referred to a higher level of care on Day 0
- § Average length of stay (in days) of children admitted to hospital
- § Proportion of children attending scheduled follow-up at the same facility by Day 7
- § Proportion of children presenting for unscheduled follow-up to any health facility by Day 7

Other outcomes of interest – antimicrobial prescription

- § Proportion of children prescribed an antibiotic at Day 0
- § Proportion of children prescribed a diagnosis-appropriate antibiotic
- § Proportion of febrile children tested for malaria at Day 0
- § Proportion of malaria positive children prescribed an antimalarial
- § Proportion of malaria negative children prescribed an antimalarial
- § Proportion of untested children prescribed an antimalarial

Other factors for exploratory analyses

- § Additional socio-demographic characteristics, urban / rural location, distance from health facility, key household indicators such as maternal age and education
- § Main complaint / symptom categories (including cough / difficulty breathing, fever, diarrhoea and other) and time since onset of symptoms
- § Alternative hypoxaemia cut-offs

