6 ANALYSIS

Analyses will follow Consolidated Standards of Reporting Trials (CONSORT) guidelines [10] and will be performed and reported overall and by country.

Outcomes will be presented separately for young infants (<60 days) and older children (60 days-59 months), the malaria-related outcomes will be presented only on older children.

Results of interim analyses and DMC analyses will be presented overall in the open report and by intervention arm in the closed report.

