6.1.4 Antimalarial-related outcomes

Although the following outcomes need to share the same definition for a cross-country analysis, it is acknowledge that malaria testing strategies are different across countries. In Tanzania all febrile children (≥ 60 days) should be tested for malaria. In India febrile children should be tested only in high risk areas (or seasons), or in low risk areas if there is history of travel to a high risk area or when no other obvious cause of fever is detected. This difference will need be taken into account when reporting these outcomes. Untested febrile children will need to be described more in detail for India.

6.1.4.1 Proportion of febrile children tested for malaria at Day 0

A child will be considered to be febrile if, at Day 0, history of fever was reported by the caregiver before the consultation or temperature was recorded to be above or equal 37.5 C° or fever was recorded elsewhere in the registry (e.g. diagnosis).

A child will be considered tested for malaria if a malaria test was ordered during the consultation and a test result is available (i.e. positive, negative, invalid/indeterminate, reported but handwriting not readable).

Only febrile children will be counted in the denominator.

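### The antimalarial outcome in SAP 6.1.4.4 pools febrile and afebrile untested children, so it can fall through case mix alone if an arm tests more of its febrile children

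*SAP*

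**What the plan says.** The outcome is listed in SAP 3.1.4 as "Proportion of untested children prescribed an antimalarial", with the same title in protocol 6.4.2. In both it belongs to the other outcomes of interest and is neither primary nor secondary.

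- **Denominator.** SAP 6.1.4.4: "Only children untested for malaria will be counted in the denominator". A child is untested when "a malaria test was not ordered during the consultation or a malaria test was ordered during the consultation but a test result is not available". Fever is not mentioned.
- **Age.** SAP 6: "the malaria-related outcomes will be presented only on older children", that is, 60 days to 59 months.
- **Who is due a test.** SAP 6.1.4: "In Tanzania all febrile children (≥ 60 days) should be tested for malaria". For India: "In India febrile children should be tested only in high risk areas (or seasons), or in low risk areas if there is history of travel", or where the fever has no other evident cause.
- **Companion outcome.** For the share tested (SAP 6.1.4.1), "Only febrile children will be counted in the denominator".
- **Extra description.** SAP 6.1.4: "Untested febrile children will need to be described more in detail for India". No denominator is set, and Tanzania is not included.
- **Comparison.** SAP 6.2.1 evaluates other binary outcomes between arms with the same random-effects logistic model as the primaries.
- **Eligibility.** SAP 5.2 enrols children with any illness, so afebrile children enter the trial.

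**The concern.** The denominator mixes children who were due a test and did not get one with children for whom fever-based policy called for no test. The mix depends on how many febrile children were tested, which happens after allocation and may differ by arm.

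The clearest route is the decision algorithm. Protocol 6.3 says it will carry recommendations on point-of-care tests, malaria among them, where these are routinely available. That arm exists only in Tanzania.

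If testing differs, the modelled odds ratio for this outcome reflects two things at once: how untested children are treated, and how many febrile children remain untested. A reader could credit the tool with changing prescribing to untested children when the change is in testing, which 6.1.4.1 already reports.

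**Working it through.** The documents state no fever, testing or prescribing rate for this outcome, so there is no planned figure to reproduce. All rates below are assumptions.

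**Notation**, for recruited children aged 60 days to 59 months: f = share febrile; t = share of febrile children tested; s = share of afebrile children tested; q and r = share prescribed an antimalarial among untested febrile and untested afebrile children.

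**SAP proportion**

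P = [f(1−t)q + (1−f)(1−s)r] / [f(1−t) + (1−f)(1−s)]

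Equivalently, P = wq + (1−w)r, where w is the febrile share of the untested. With s fixed, raising t lowers w, so P falls if q > r, is unchanged if q = r, and rises if q < r.

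**Main example:** f = 60%, q = 20%, r = 0, s = 0.

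- Control, t = 70%: untested febrile 0.6 × 0.3 = 0.18; untested afebrile 0.40; P = 0.18 × 0.2 / 0.58 = 0.036/0.58 = 6.2%.
- Intervention, t = 90%: untested febrile 0.6 × 0.1 = 0.06; P = 0.012/0.46 = 2.6%.
- Odds ratio = (0.012/0.448) / (0.036/0.544) = 0.40.
- Among untested febrile children: 20% v 20%.
- Over all recruited older children: 3.6% v 1.2%; odds ratio = (0.012/0.988) / (0.036/0.964) = 0.33.

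**Sensitivity to r.** The last column covers f = 40% to 70% with testing of 70% v 90%, 80% v 90% and 50% v 80%; q = 20% throughout.

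| r | Main example | Odds ratio | Odds ratio over the grid |
|---|---|---|---|
| 0% | 6.2% v 2.6% | 0.40 | 0.37 to 0.58 |
| 2% | 7.6% v 4.3% | 0.55 | 0.55 to 0.75 |
| 5% | 9.7% v 7.0% | 0.70 | 0.68 to 0.87 |
| 20% (= q) | 20% v 20% | 1.00 | 1.00 |

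**Where the extra tests go matters.** Take f = 60%, t = 50%, q = 30%, r = 2%, and put the extra tests only in afebrile children (s from 0 to 40%). P goes from (0.090 + 0.008)/0.70 = 14.0% to (0.090 + 0.0048)/0.54 = 17.6%. Here more testing raises the figure.

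**The case against.** The strongest case on the other side has four parts.

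**The definition is faithful.** SAP 6.1.4.4 implements the outcome title literally, as the protocol lists it. A prescription to an untested afebrile child is also of interest, and a febrile-only version would drop it. This stands: the weakness is in interpretation, and nothing here is a contradiction between protocol and SAP.

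**The SAP already responds in part.** It reports testing alongside, says the differing national testing strategies must be considered in reporting, and promises more detail on untested febrile children in India. This helps, but it sets no denominator and omits Tanzania, the only country with the algorithm arm.

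**A testing gap is not documented for most comparisons.** A reader might infer that the interventions in general are meant to change malaria testing. The documents support a route only for the algorithm arm. Oximetry alone adds a device and job aid, and protocol 6.3 gives guideline refresher training in every arm to control for its effect.

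**Dividing by all recruited older children does not isolate prescribing either.** It moves with testing too, and in the main example its odds ratio is further from 1 (0.33 v 0.40). This stands. Its merit is that it does not select children on a post-allocation event; it gives the combined effect of testing and prescribing and must be labelled so.

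**Conclusion.** The point holds conditionally. The proportion in SAP 6.1.4.4 falls through case mix alone when two conditions are met: untested febrile children receive antimalarials more often than untested afebrile children, and an arm tests more of its febrile children. The first is likely under a fever-based testing policy. The second is plausible mainly for the algorithm arm v control in Tanzania.

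With no afebrile child treated, the odds ratio is 0.37 to 0.58 over the grid when the rate in untested febrile children is the same in both arms. With 5% of afebrile children treated it is 0.68 to 0.87.

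Three stronger readings are tempting and unsupported:

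- That the figure falls whenever an arm tests more. It is unchanged if both groups are treated alike, and can rise if the extra tests go to afebrile children.
- That the apparent reduction is always half or more. Even with no afebrile child treated, the smallest relative fall in the grid is 41% (6.4% to 3.8%, at 70% febrile and testing of 80% v 90%).
- That most of the denominator was never due a test. The documents give no rates. With 40% to 70% febrile and 50% to 90% of them tested, the afebrile share of the untested runs from 46% to 94%.

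The fall in antimalarials given without a test, per recruited child, is real in the example (3.6% v 1.2%). The error would be to read the SAP figure as a change in how untested children are treated. This is a minor point on a supporting outcome.

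**What to change.** In SAP 6.1.4.4:

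1. Report by arm, in both countries, the number of untested febrile children and the proportion of them prescribed an antimalarial, using the fever definition in 6.1.4.1.
2. Report antimalarial without a test over all recruited children aged 60 days to 59 months as the between-arm comparison that does not condition on testing, and state that it combines testing and prescribing effects.
3. Keep the all-untested proportion as a descriptive line, with a note that it is not to be read alone as a prescribing change.

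The cost is SAP wording and two extra columns. Fever, test and prescription data are already collected, and the SAP already reports second denominators elsewhere (for example 6.1.2.3, 6.1.2.6 and 6.1.5.4). The limitation is that the febrile-only figure still conditions on a post-allocation event, so it should stay descriptive.

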6.1.5 Hypoxaemia-related outcomes – only in intervention arms

6.1.5.1 Proportion of children with severe, moderate and mild hypoxaemia, adjusted for sites at high altitude

Hypoxaemic children will be summarised disaggregated by groups based on the following SpO₂ values ranges: SpO₂ < 90%, 90% ≤ SpO₂ < 92% and 92% ≤ SpO₂ < 94%. All children recruited will be in the denominator.

All facilities in India and Tanzania are in low altitude area and therefore no adjustment is required.

6.1.5.2 Proportion of children with hypoxaemia (according to differing cut-offs) with severe complication

Children with severe complication will be summarised disaggregated by groups based on the following SpO₂ values ranges: SpO₂ < 90%, 90% ≤ SpO₂ < 92% and 92% ≤ SpO₂ < 94%. spurious values and missing values. Each SpO₂ group will be the denominator of each proportion.

6.1.5.3 Proportion of children with severe hypoxaemia not meeting any other clinical criteria for severe disease

Children with severe hypoxaemia (according to country's specific cut-off) not meeting any other clinical criteria for severe disease will be counted in the numerator. All children recruited will be in the denominator.

Severe disease will be defined in a separate document.

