To assess severe, moderate and mild hypoxaemia prevalence among sick children attending intervention primary care facilities, and understand the association of different hypoxaemia cut-offs with adverse outcomes, according to sociodemographic and clinical features.

Implementation and process

- To understand the facilitators and barriers to uptake, acceptability of the intervention and behaviour change by health care providers, caregivers and their children, and a variety of stakeholders at community, health facility, national and international levels
- To evaluate characteristics of children, caregivers, healthcare providers and health facilities associated with uptake and impact of the interventions
- To understand how the interventions affect patient flow and patient-provider interactions, including change in care processes, consultation time, and communication between caregivers and healthcare providers

Cost and cost-effectiveness

- To determine the cost and estimate any cost savings and/or additional costs of introducing pulse oximetry with or without CDAs into primary care in four countries
- To estimate cost effectiveness of the interventions compared to routine care and other interventions aimed at improving the management of severe illness in children 0 – 59 months of age

5 Study design

Health and quality of care impact are evaluated through pragmatic, parallel group, cluster randomised controlled superiority trials in India and Tanzania, and quasi-experimental pre-post studies in Kenya and Senegal.

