8.3.3 Cost and cost-effectiveness study

When all the cost components have been collected, the data will be aggregated or collated in Excel. Once the summary is completed, a cost profile of the programme activities will be derived and after the total costs of the programme have been calculated, the unit costs will then be derived (i.e. total costs divided by the sample size). These profiles are useful in highlighting major cost components (and thus identifying potential areas where improvements in efficiency may have significant impact on costs). For this evaluation, analysis will focus on full costing and incremental costing approach. Total, average and incremental costs per year will be estimated. Costs associated with increasing the oxygen saturation referral threshold will be estimated based on the additional proportion of children meeting referral criteria.

When available, effectiveness data will be combined with the cost data and cost per DALY averted will be estimated. Effectiveness will be modelled using the information on severe outcomes such as mortality, and secondary hospitalization, adjusting as far as possible the level of severity of illness of the child at presentation.

At primary care facilities, these will include measurements (when taken by healthcare providers) such as anthropometry, respiratory rate, temperature and routine investigations where available (e.g. haemoglobin, CRP), and oxygen saturation (post-intervention/in intervention arms). We will also use diagnosis and severity classification recorded by primary care providers.

At hospital level, we will also utilize the same measurement data, and other vital sign data (such as a paediatric early warning score if recorded), decision to admit, intensive care and / or ventilation, provisional and final diagnosis, admission outcome (discharge, death, left against medical advice) and length of hospital stay. We will then use these indicators, along with mortality from phone call follow-up data by Day 28, to predict probability of mortality based on available literature. The DALY calculation will be based primarily on probability of mortality

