6.1.1 General definitions

Day 7 / Day 28 assessment

Day 7 / Day 28 assessment refers to information reported by the caregiver after Day 0 and recorded in Day 7 / Day 28 forms. Data collected as part of unscheduled visits are also integrated in these forms.

If multiple successful follow-up assessments for the same child are recorded within Day7 or Day28 databases, the most recent follow-up assessment within each database will be used. To limit potential recall bias, assessments conducted far beyond the expected follow-up time will be dropped. This will be 30 and 60 days from Day 0 for Day 7 and Day 28 respectively.

Death

A child will be considered deceased if, from Day 7 / Day 28 assessment, his/her status at the time of follow-up is “deceased”. In case of implausible death date (i.e. prior to enrolment date), death will be handled as follow:

- ξ if death date is recorded at Day7 follow-up, death will be assumed to be within 7 days of Day0
- ξ if death date is not recorded at Day7 follow-up but only at Day28 follow-up, death will be assumed to be after 7 days of Day0 but within 28 days.

Hospitalisation

A child will be considered hospitalised if, from Day 7 / Day 28 assessment, he/she went to a hospital, was admitted overnight or if his/her status at the time of follow-up is “hospitalised”. In case of implausible hospitalisation date (i.e. prior to enrolment date), hospitalisation will be handled as follow:

- ξ if hospitalisation date is recorded at Day7 follow-up, hospitalisation will be assumed to be within 7 days but after 24hrs of Day0
- ξ if hospitalisation date is not recorded at Day7 follow-up but only at Day28 follow-up, hospitalisation will be assumed to be after 7 days of Day0 but within 28 days.

Hospitalisation within 24hrs of Day0

For the purpose of primary analysis, a child will be considered admitted to hospital 24hrs of Day0 consultation if the date of hospitalisation is the same as Day0 date or is one day after Day0 date.

Referral

A child will be considered to be referred (either to a hospital or to an inpatient part of a larger primary healthcare facility) if, at Day0, the caregiver confirms that the child was urgently referred or the research assistant confirms that an urgent referral advice was recorded for the child. If urgency is unknown from both sources, referral will be assumed to be urgent.¹

Antibiotics

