6.1.2 Health, hospitalisation and referral outcomes

6.1.2.1 Proportion of children with a severe complication by Day 7

Severe complication is defined as death or secondary hospitalisation. Secondary hospitalisation refers to any delayed hospitalisation (occurring at any point greater than 24hrs after the Day 0 consultation) and any hospitalisation occurring without a referral.

Information on death and hospitalisation will be taken, in order, from:

- ξ Day7 follow-up assessment
- ξ If Day7 follow-up assessment is missing, Day28 follow-up assessment

Death will be counted in the numerator if death date is within 7 days of Day0 (7th day included). Hospitalisation will be counted in the numerator if the child was not referred at Day0 or hospital admission date is within 7 days of Day0 (7th day included) but after 24hrs of Day0.

The denominator will be all children recruited. Children for whom no death and hospitalisation data are available or withdrew prematurely from the study will be assumed to be alive and not hospitalised by Day7.

6.1.2.2 Proportion of children with a severe complication by Day 28

Severe complication is defined as per the outcome above.

Information on death and hospitalisation will be taken, in order, from:

- ξ Day7 follow-up assessment
- ξ If Day7 follow-up assessment is missing or no outcomes were reported, Day28 follow-up assessment
- ξ If both Day7 and Day28 assessments are missing or no outcomes were reported, unscheduled visits (deaths only)

Death will be counted in the numerator if death date is within 28 days of Day0 (28th day included). Hospitalisation will be counted in the numerator if the child was not referred at Day0 or hospital admission date is within 28 days of Day0 (28th day included) but after 24hrs of Day0.

The denominator will be all children recruited. Children for whom no death and hospitalisation data are available or withdrew prematurely from the study will be assumed to be alive and not hospitalised by Day28.

6.1.2.3 Proportion of children admitted to hospital within 24 hours of Day 0 consultation and as a result of a referral

Information on hospitalisation will be taken, in order, from:

- ξ Day7 follow-up assessment
- ξ If Day7 follow-up assessment is missing, Day28 follow-up assessment

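### The SpO2-band table in SAP 6.1.5.2 counts severe complications, which leave out prompt admissions after referral, so it tends to understate risk below 90% relative to the neighbouring bands

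*SAP*

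**What the plan says.** Protocol section 4 sets an objective to "understand the association of different hypoxaemia cut-offs with adverse outcomes". SAP 6.1.5.2 is the listed outcome closest to it. It applies to the intervention arms only: "Children with severe complication will be summarised disaggregated by groups based on the following" SpO2 ranges (below 90%, 90 to under 92%, 92 to under 94%), with spurious and missing values as further groups. "Each SpO₂ group will be the denominator of each proportion". No time point is named there.

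The outcome is defined in SAP 6.1.2.1: "Severe complication is defined as death or secondary hospitalisation". Secondary hospitalisation covers late admissions and "any hospitalisation occurring without a referral". In operational terms: "Hospitalisation will be counted in the numerator if the child was not referred at Day0 or hospital admission date is within 7 days", with the further condition that a referred child's admission falls after the first 24 hours. SAP 6.1.1 puts an admission inside those 24 hours "if the date of hospitalisation is the same as Day0 date or is one day after Day0 date".

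Protocol 6.3 advises providers to refer at SpO2 below 90%, and to go on referring children who have other signs. Between 90% and 93%, SpO2 alone prompts no referral.

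**The concern.** This point is about comparing SpO2 bands within the intervention arms. It does not question severe complication as an outcome for comparing arms.

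In the band table, whether an admission counts depends on referral, and referral is advised because of the very measurement that defines the bands. A child at 89% who is referred and admitted that day is a non-event. A child at 91% who is admitted that day without a referral is an event. If referral is more common below 90%, as intended, more admissions drop out of that band than out of the bands above it. The contrast is then pulled towards no difference, and possibly past it. A reader of the table could conclude that children just above 90% fare about as badly as those below, when part of the similarity comes from the counting rule.

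**Working it through.** **1. How the definitions score individual children (all alive at the time point)**

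| Child | Referred at Day 0 | Admitted | Severe complication? |
|---|---|---|---|
| SpO2 89% | yes | Day 0 or Day 1 | no |
| SpO2 89% | yes | Day 3 | yes |
| SpO2 91% | no | Day 0 or Day 1 | yes |
| SpO2 91% | yes (other signs) | Day 0 or Day 1 | no |

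The rule is the same in every band. What differs is the chance of being referred.

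**2. Planning rates.** The plan gives no figure for this table, so I checked that the planning rates in SAP 3.4 are coherent. Inputs: severe complication 1.1% v 0.77%, 80% power, alpha 0.05 (two-sided assumed), ICC 0.001, cluster sizes 510 (India) and 1680 (Tanzania).

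- n per arm = [1.960 × √(2p̄(1−p̄)) + 0.842 × √(p₁(1−p₁) + p₂(1−p₂))]² / (p₁−p₂)² = 13,351.
- India: design effect 1 + 509 × 0.001 = 1.509. 13,351 × 1.509 = 20,147, and 20,147/510 = 39.5, so 40 clusters, as stated for the three-arm calculation.
- Tanzania: design effect 1 + 1679 × 0.001 = 2.679. This gives 35,768 children, and 35,768/1680 = 21.3, so 22 clusters, as stated.
- For prompt referred admission (1.5% v 1.95%), the same steps give 39 and 21 clusters, which the stated numbers cover.

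Share of the two outcomes combined that severe complication leaves out, over all enrolled children:

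- control: 1.5/(1.5 + 1.1) = 58%
- intervention at the design effect: 1.95/(1.95 + 0.77) = 72%

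These sums ignore the small overlap of children who die after a prompt admission. They are not rates for any SpO2 band.

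**3. Direction.** Within a band, let h be the proportion admitted by Day 7, q the share of admitted children who were referred, c the share of referred admissions that were prompt, and d the proportion dying without admission.

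- death or any admission = h + d
- severe complication ≈ h(1 − qc) + d (deaths after a prompt referred admission would add slightly)

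The admission part of the ratio between two bands is multiplied by (1 − q₁c₁)/(1 − q₂c₂). This factor is below 1 whenever qc is larger in the lower band. For example, with q = 70% below 90%, q = 15% above and c = 90% in both, it is 0.37/0.865. A true admission ratio of 0.865/0.37 = 2.34 would then show as 1.0.

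**4. Illustration. All inputs are assumed.** h = 40% below 90% and 15% at 90–91%; d = 2% and 1%; q = 15% at 90–91%; the same c in both bands. The ratio of death or any admission is 42%/16% = 2.6.

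| q below 90% | c | Severe complication below 90% | At 90–91% | Ratio |
|---|---|---|---|---|
| 15% (equal) | 90% | 0.40 × 0.865 + 0.02 = 36.6% | 0.15 × 0.865 + 0.01 = 14.0% | 2.6 |
| 30% | 50% | 0.40 × 0.85 + 0.02 = 36.0% | 0.15 × 0.925 + 0.01 = 14.9% | 2.4 |
| 38% | 90% | 0.40 × 0.658 + 0.02 = 28.3% | 14.0% | 2.0 |
| 59% | 90% | 0.40 × 0.469 + 0.02 = 20.8% | 14.0% | 1.5 |
| 70% | 70% | 0.40 × 0.51 + 0.02 = 22.4% | 0.15 × 0.895 + 0.01 = 14.4% | 1.6 |
| 70% | 90% | 0.40 × 0.37 + 0.02 = 16.8% | 14.0% | 1.2 |
| 90% | 90% | 0.40 × 0.19 + 0.02 = 9.6% | 14.0% | 0.69 |

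The 38% and 59% rows borrow from Protocol 3.2, which reports 38% of children with severe disease referred in a Tanzanian study and 41% of those with severe or very severe pneumonia not referred in a Malawian one. Those were routine-care settings and a different denominator, so they are only a rough guide.

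**5. What the SAP offers elsewhere.** SAP 6.1.5.4 reports hypoxaemic children who were referred, and who were referred and admitted, but at the country's cut-off and not by band. The Day 0, 3-day and 7-day admission windows in SAP 6.2.4 apply to the primary outcomes only. Work on other hypoxaemia thresholds is deferred to a separate document (SAP 3.1.4). None of these gives all admissions by SpO2 band.

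**The case against.** The other side has a good deal of substance, and it rules out several stronger readings.

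- *A reader might infer that the main adverse outcome has been removed below 90%.* Deaths, delayed admissions and unreferred admissions count in every band. Referral is advice and will not be universal, and children above 90% with other signs are to be referred too. Protocol 6.4.2 treats prompt admission after referral as a proxy for appropriate referral, an intended effect.
- *A reader might infer that the cut-off question is answered wrongly, or that the gradient reverses.* The table is descriptive, belongs to the other outcomes of interest and has no decision rule attached. Further threshold work and prognostic modelling (Protocol 8.3.2) are planned. Among the scenarios above, reversal appears only when referral and prompt admission are both at 90%.
- *A reader might infer that the cost study inherits the problem.* Protocol 8.3.3 says: "Costs associated with increasing the oxygen saturation referral threshold will be estimated based on the additional proportion of children meeting referral criteria". That is a prevalence, not an outcome by band. Nothing in the documents feeds this table into the cost model.
- *A reader might infer that death or any admission is the clean replacement.* It is not. Referral leads to admission, so any admission can be higher below 90% because of the referral advice itself.

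SAP 6.1.5.4 also makes many of the omitted admissions visible at the country's cut-off. That narrows the gap, but it gives no comparison with the 90–91% and 92–93% bands. The direction of the bias is untouched by these points.

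**Conclusion.** The point holds as a matter of direction. As defined, the table tends to understate risk below 90% relative to the neighbouring bands, and it cannot by itself inform the objective on cut-offs and adverse outcomes. This rests on one assumption, which the plan intends to make true: among admitted children, the combination of referral and prompt admission is more common below 90% than above. The size is unknown, because the documents give no referral or prompt-admission rates by SpO2 band. In the illustration a ratio of 2.6 is unchanged if referral is equal, falls to between 2.4 and 1.2 in the intermediate scenarios, and reverses to 0.69 only at the extreme. The 58% to 72% share shows that the omitted admissions are the larger part over all enrolled children on the planning rates. It says nothing direct about any band. The primary analysis is not affected.

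**What to change.** In SAP 6.1.5.2, keep severe complication as listed, state its time point, and add for each SpO2 band:

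1. death by Day 7 and death by Day 28, using the date of death from whichever follow-up recorded it, as SAP 3.8 provides. This is the only outcome here whose classification does not depend on referral status;
2. any hospital admission by Day 7, split into prompt referred admission and secondary hospitalisation;
3. death or any admission by Day 7.

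Add a sentence saying that referral itself raises any admission, while severe complication drops prompt referred admissions, so the two are biased in opposite directions and should be read together.

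The cost is a short SAP edit and a few descriptive columns from data already collected. There will be few deaths per band, so those columns will be imprecise. The primary outcomes, sample size and trial procedures do not change, and no referral threshold is proposed.
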